5.4 Derivation of index values and scores

For details on handling of missing items and derivation of scores refer to the document "Handling of missing items and derivation of total scores". The most recent version of this document stored at [REDACTED]

[REDACTED] available before the database lock will be used as reference.

5.4.1 11-point Numeric Rating Scale (NRS)

The Numeric Rating Scale (NRS) is an 11–point scale for patient self-reporting of pain. The averaged score will be computed for every week, regardless of visits.

24-hour Average Pain Score

The 24-hour average pain score will be assessed using the 11-point numeric rating scale (NRS) scale ranging from zero to ten.

24-hour Worst Pain Score

The 24-hour worst pain score will also be assessed using the 11-point NRS scale ranging from zero to ten.

5.4.2 Verbal Rating Scale (VRS) pain intensity

The Verbal Rating Scale (VRS) is a questionnaire administered by the clinician to capture the patient's level of pain. The response will be recorded as 0 = none, 1 = mild, 2 = moderate, and 3 = severe. The score is recorded at baseline only.

5.4.3 Brief Pain Inventory- Short Form (BPI-SF)

Patients will be asked to complete the 7-item pain interference scale which assesses the degree to which pain interferes with walking and other physical activity, work, mood, relations with others and sleep using a zero to ten numeric rating scale, with zero being "does not interfere" and ten being "completely interferes". The score is recorded at Visits 101, 104, 106, 199, TD visit.

The BPI interference total score will be derived as the sum of the 7 responses for the questions 9A-9G. The total score ranges from 0 to 70.

5.4.4 Patient Global Impression of Change (PGIC)

The Patient Global Impression of Change (PGIC) is a patient-reported instrument that measures change in overall status on a scale ranging from one ("very much improved") to seven ("very much worse"). The score is recorded at Visit 199 and TD visit only.

5.4.5 Neuropathic Pain Symptom Inventory (NPSI)

The Neuropathic Pain Symptom Inventory (NPSI) is a 12 item patient reported outcome measure that contains 10 descriptors representing 5 dimensions of pain (burning pain, deep/pressing pain, paroxysmal pain, evoked pain and paraesthesia/dysesthesia) and 2 temporal items designed to assess pain duration and the number of pain paroxysms. The score is recorded at Visits 101, 104, 106, 199, 201 and TD visit.

The sum of the responses to the 10 questions (all except qn. 4 and qn. 7) will be regarded as the total score and will be used for the analysis.

[figure not shown]
[figure not shown]
The dimensional score of each of the five dimensions are calculated as follows :

[figure not shown]
[figure not shown]
- Burning = Q1
- Pressing = (Q2 + Q3) /2
- Paroxysmal = (Q5 + Q6) /2
- Evoked = (Q8 + Q9 + Q10) /3
- Paraesthesia / dysesthesia = (Q11 + Q12)/2

5.4.6 Insomnia Severity Index (ISI)

Patients will be asked to complete the ISI using five-point Likert-style scale as a measure of perceived sleep difficulties. Scores can range from zero to 28, with a cut-off score of eight suggesting the presence of sub-threshold insomnia. The questionnaire assesses the severity of insomnia, satisfaction with current sleep pattern, sleep interference, "noticeability" of sleeping problem to others and concern about sleeping problems. The score is recorded at Visits 101, 199 and TD visit.

The sum of seven responses represents the total score. Each of the 7 items is scored using a range from 0 to 4, thus the total score values can range from zero to 28.

5.4.12 Douleur Neuropathique 4 (DN4)

The Douleur Neuropathique 4 (DN4) is a clinician administered questionnaire that can be useful in diagnosing neuropathic pain (Bouhassira et al 2005). DN4 consists of 10 items. Seven items are related to pain quality and are based on an interview with the patient, and 3 items are based on the clinical examination. This score is recorded at Screening only. Each of the 10 items has a dichotomous answer Yes (=1) or No (=0). The global score is calculated as the sum of the 10 items.

5.5 Statistical models

SAS codes for all statistical methodology described in this section will be included as programming note in TFL Shells.

5.5.1 Primary analysis

5.5.1.1 ANCOVA

The primary analysis (and all other analyses of continuous variables) will be done using analysis of covariance. The model is:

mean pain score = intercept + treatment + sex + age + PDNmed (yes/no) + baseline (mean pain intensity) + error.

The SAS procedure MIXED will be used for computing p-values and 95% confidence intervals for LS means.

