9.4.2 Statistical model, hypothesis, and method of analysis

The aim is to estimate the treatment effect of the investigational drug (EMA401) compared to placebo, for the target population on the primary pain parameter. The definition and the justification of the corresponding primary estimand, as well as the definition of the supplementary and secondary estimands for NRS are detailed in an Estimand Charter. The definitions of the estimands for the key secondary variable NPSI will also be detailed in an Estimand Charter.

Summary statistics by treatment and visit will be provided for the primary and key secondary efficacy variables.

The primary estimation method for the both primary and key secondary efficacy variable will be based on an Analysis of Covariance (ANCOVA) model including region (e.g. US, EU), treatment, sex, use of concomitant pain medication for PDN (yes/no) as factors and baseline score of the corresponding scale and age as covariate in an univariate fashion. The analysis will account for different post-randomization events as follows:

- **Changes in doses of concomitant medication for PDN:** Efficacy observations collected during the period of changes in doses of concomitant medication for PDN (compared to baseline) and the 3-days thereafter will be excluded, since they are considered affected by the concomitant medication dose change. The resulting missing data after this step will be imputed via multiple imputation method using the Missing at random (MAR) assumption.
- **Intake of rescue medication:** Efficacy data collected during intake of rescue medication will be used for analysis.
- **Intake of prohibited medications with potential confounding effect prior to study treatment discontinuation:** The prohibited medications with a potential confounding effect are defined as those listed in [Table 5-2](#) requiring study treatment discontinuation. Efficacy observations collected during the intake period of such prohibited medications and the 7-days thereafter will be excluded, since they are considered affected by the prohibited medication intake. The resulting missing data after this step will be imputed via multiple imputation method using the MAR assumption.

The design feature of retrieved drop-outs, considered in order to minimize the occurrence of missing data on primary pain parameter, is exploited for the statistical analysis as follows:

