9.8 Sample size calculation

The calculation of power for the testing procedure mentioned in [Figure 9-1](#) is based on the following assumptions:

- The treatment difference of 100 mg b.i.d. vs. placebo was assumed as 0.7, 0.8 and 0.9 points, for the primary efficacy variable (weekly mean of the 24-hour average pain score). A treatment difference of 0.7 points was observed for the 100 mg b.i.d. dose vs. placebo for weekly mean of the 24-hour average pain score (NRS) in the Study EMA401-003 during a 4-week treatment period. The standard deviation is 2.6 points (based on data from pregabalin historical trials – see [FDA Approval Package Medical Review, 2004](#)) is assumed for the primary efficacy variable. In Study EMA401-003 in PHN patients, a standard deviation of approximately 2.0 points was observed. A

slightly higher value of 2.6 has been chosen to account for a possible higher variability due to a higher number of centers and due to multiple imputations (as opposed to single imputation) in the analysis. It is also assumed that the same standard deviation holds for the PDN population.

- Treatment differences of 5 points for Pregabalin and 10 points for Duloxetine on NPSI total score were observed via an indirect comparison using the results from [Tesfaye \(2013\)](#) which is an active control study (Pregabalin vs Duloxetine) and [Kalliomaki \(2013\)](#) which is a placebo controlled study (AZD2423 vs placebo). The standard deviation was derived as 16 points using the results from [Kalliomaki \(2013\)](#). A correlation of approximately 0.2 was observed between the baseline scores of NRS and NPSI total score in [Freeman et al \(2014\)](#). The power of the study was calculated assuming correlation coefficient values of 0 and 0.2. Since the power values obtained for correlation values of 0.2 and 0 are similar, in a conservative scenario the results reported herein are for correlation value of 0.

Since the NPSI has not been studied in the EMA401-003 study, to mitigate the risk of uncertainty on the value of treatment difference and standard deviation, the effect size (treatment difference/ standard deviation) of NPSI total score has been considered for the calculation of power. The power of the study was calculated for different effect sizes ranging in 0.1, 0.5 for NPSI total score corresponding to 100 mg.

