2.6.2 Statistical hypothesis, model and method of analysis

To compare the efficacy of EMA401 over placebo in the NPSI total score the null hypothesis of superiority of EMA401 over placebo will be tested. The definitions of the estimands for the key secondary variable NPSI will also be detailed in an Estimand Charter.

The estimation of the treatment difference and missing data handling will be performed using the method of analyses mentioned for the primary analysis for NRS. Post randomization events will be handled in the same way as in the primary analysis for NRS.

The key secondary objective will be achieved if the EMA401 100 mg b.i.d. dose is statistically significant versus placebo in terms of NPSI total score after multiplicity adjustment. To preserve the family-wise error rate at the 2.5% level when comparing the EMA401 100 mg b.i.d. dose versus placebo on the two endpoints NRS and NPSI, statistical testing will be carried out using the graphical testing procedure as explained in Section 2.5.2.

The same ANCOVA model will be applied at the visits prior to Week 12. Multiplicity adjustment at visits prior to Week 12 will not be carried out.

The same supplementary analysis as for the primary endpoint will be performed.

Summary statistics by treatment and visit will be provided for the key secondary endpoint.

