5.5.1.2 Missing data imputation

For the purpose of missing data imputation, the following two scenarios will be considered:

- Jump to reference (J2R)
- Missing At Random (MAR)

The imputation will be based on all available data (i.e. from all scheduled time points) using all covariates as specified in the ANCOVA model. For J2R only placebo data will be used, for MAR data from the same treatment arm will be used for building the imputation model.

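### The protocol adjusts NPSI for its own baseline, but the SAP's only written ANCOVA, reused for the NPSI key secondary test, names just the NRS baseline

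*SAP*

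**What the plan says.** **Protocol 9.4.2** covers both endpoints: "The primary estimation method for the both primary and key secondary efficacy variable will be based on an Analysis of Covariance (ANCOVA) model". The baseline term is the "baseline score of the corresponding scale and age as covariate in an univariate fashion". For NPSI that means baseline NPSI total score.

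**SAP 2.5.2** lists treatment, sex, concomitant PDN medication, age and the baseline mean pain intensity score. The reference to the corresponding scale is gone.

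**SAP 5.5.1.1** opens with "The primary analysis (and all other analyses of continuous variables) will be done using analysis of covariance" and then gives a single equation: "mean pain score = intercept + treatment + sex + age + PDNmed (yes/no) + baseline (mean pain intensity) + error". Mean pain intensity is the NRS quantity.

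**SAP 2.6.2** says that NPSI estimation and missing-data handling "will be performed using the method of analyses mentioned for the primary analysis for NRS". It repeats the same ANCOVA for earlier visits, adds the same supplementary analysis, and names no baseline NPSI term.

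**SAP 5.5.1.2** builds the imputation model "using all covariates as specified in the ANCOVA model".

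**SAP Section 4**, which lists departures from the protocol, records one change to the ANCOVA covariates: region is removed.

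**The concern.** The two documents name different baseline covariates for an alpha-controlled test, and nothing explains the difference. After Amendment 1 dropped the ANCOVAs for BPI-SF, worst NRS pain and ISI, NPSI is the only other named continuous efficacy endpoint still tested this way, so the gap falls on the key secondary hypothesis.

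Baseline NRS is a poor stand-in. The protocol's own sample size section reports that "A correlation of approximately 0.2 was observed between the baseline scores of NRS and NPSI total score". An NPSI model without baseline NPSI gives up most of the precision that baseline adjustment is meant to provide, and it does not correct a chance imbalance in baseline NPSI. Only 137 of the planned 400 patients were randomized, so precision is scarce and chance imbalance is larger than planned for.

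**Working it through.** **1. The plan's power figures.** No stated figure is disputed; this step confirms the setting. Inputs (Protocol 9.8, SAP Section 3): 200 per arm, one-sided alpha 0.025, NRS difference and SD, NPSI effect size, endpoint correlation 0. Power is Φ(d·√(n/2) − 1.96), with d the difference divided by the SD. Key secondary power is the product of the two powers.

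| NRS difference / SD, NPSI effect size | Primary: computed (stated) | Key secondary: computed (stated) |
|---|---|---|
| 0.8 / 2.6, 0.40 | 86.8% (85%) | 85.0% (84%) |
| 0.7 / 2.6, 0.35 | 76.8% (77%) | 72.1% (72%) |
| 0.9 / 2.6, 0.45 | 93.3% (94%) | 92.8% (93%) |

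All agree within two points.

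**2. Precision lost with the wrong baseline.** From the documents: baseline NRS–NPSI correlation 0.2. Assumed:
- NPSI has equal variance at baseline and Week 12 (set to 1).
- The baseline to Week 12 NPSI correlation ρ is 0.3 to 0.7.
- Baseline NRS predicts Week 12 NPSI only through baseline NPSI, so its correlation with Week 12 NPSI is 0.2ρ.

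Residual variances:
- Adjusted for baseline NPSI: 1 − ρ²
- Change in NPSI, adjusted for baseline NRS only: 2(1 − ρ) − [0.2(1 − ρ)]²

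| ρ | NPSI baseline | NRS baseline only | Variance ratio | Standard error ratio |
|---|---|---|---|---|
| 0.3 | 0.91 | 1.40 − 0.0196 = 1.3804 | 1.52 | 1.23 |
| 0.5 | 0.75 | 1.00 − 0.0100 = 0.9900 | 1.32 | 1.15 |
| 0.7 | 0.51 | 0.60 − 0.0036 = 0.5964 | 1.17 | 1.08 |

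At ρ = 0.5 the loss is like analysing 137 / 1.32 ≈ 104 patients.

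**3. What that means for power.** Take the NPSI effect size of 0.4 on the residual SD of the model with baseline NPSI, complete data, and 137 / 2 = 68.5 per arm. Marginal NPSI power with baseline NPSI is Φ(0.4·√34.25 − 1.96) = 64.8%. Dividing the effect by the standard error ratios gives 47.6%, 53.1% and 58.1% for ρ = 0.3, 0.5 and 0.7, a loss of about 7 to 17 percentage points.

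**4. Which response is modelled.** SAP 2.6.1 defines the endpoint as change in NPSI total score; the equation in 5.5.1.1 has a score on the left. With baseline NPSI in the model this does not matter: the baseline coefficient shifts by exactly 1 and the treatment estimate is identical. Without it, the two estimates differ by the adjusted chance difference in baseline NPSI between arms. The unadjusted standard error of that difference is √(2 / 68.5) = 0.17 baseline SDs.

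**The case against.** The strongest reply is that the equation cannot be literal for NPSI. It sits under the primary analysis and its response is the mean pain score, so applied word for word to NPSI it would test NRS again. It must be a template, and if the response is swapped for the scale analysed, the baseline should be swapped too. That gives the protocol's model. SAP Section 4 points the same way: it lists changes and does not say that baseline NPSI was dropped. The Estimand Charter and the SAS code in the TFL shells, neither of them available here, may settle it. This stands as to likely intent. It does not remove the gap, because nowhere does the SAP tell the programmer to swap the covariate, and the protocol's words that did so are missing.

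Three stronger readings are tempting and are not supported:
- **That the sponsor decided to drop baseline NPSI.** No passage says so; loose reuse of the NRS wording is the simpler explanation.
- **That imputation will ignore baseline NPSI.** SAP 5.5.1.2 also uses all available data from all scheduled time points, and NPSI is recorded at Visit 101, so baseline NPSI may enter that way. It is only not named as a covariate.
- **That the standard error could rise by as much as 39%.** That figure needs a raw Week 12 response at ρ = 0.7: √(0.9804 / 0.51) = 1.39. The specified endpoint is a change.

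It is also fair to say that the consequence is bounded. NPSI is tested only after NRS succeeds. With 0.8 / 2.6, 68.5 per arm and complete data, NRS power is Φ(1.80 − 1.96) ≈ 44%, so the confirmatory NPSI test would more likely than not never be reached.

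**Conclusion.** The concern holds as a conflict of wording between protocol and SAP on the key secondary model, with a real but moderate cost if the SAP is programmed as written. The choice of baseline covariate does not by itself bias the randomized comparison or inflate type I error. For the change-from-baseline endpoint the standard error would be about 8% to 23% larger than under the protocol's rule. The 0.2 correlation comes from an external study cited in the protocol; the range for ρ, the equal variances and the route from baseline NRS to Week 12 NPSI are assumptions. The text also leaves more than one possible NPSI estimate and p-value open, which a pre-specified key secondary test should not do. A reader might infer that the wrong covariate will certainly be used; the documents show only that the SAP does not rule it out.

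**What to change.** Four edits, before unblinding:
- **SAP 2.5.2 and 5.5.1.1:** replace the baseline mean pain intensity term with the baseline score of the scale being analysed, as in Protocol 9.4.2.
- **SAP 2.6.2:** write out the NPSI model, with change from baseline in NPSI total score as response and baseline NPSI total score as covariate, alongside treatment, sex, age and concomitant PDN medication.
- **SAP 5.5.1.2:** state that the NPSI imputation model includes baseline NPSI.

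Check that the Estimand Charter and the TFL-shell code agree. The cost is a few lines of text. Baseline NPSI is already collected, so no new data are needed.

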The primary analysis on the change from baseline to Week 12 in the weekly mean of the 24-hour average pain score will be performed as originally planned. Besides the primary estimand, which is of main clinical interest, the supplementary estimand, which provides insight into the magnitude of improvement in efficacy that might be achieved if all patients were able to take EMA401 as prescribed for 12 weeks, will be analysed. The other planned supplementary estimands will be dropped, as they are of minor interest in the situation with many study treatment discontinuations due to trial termination in the scope of the Urgent Safety Measures (USM).

To support the primary analysis and to get an idea about the effect that might be achieved if the trial had not been terminated and if all patients had the chance to complete the Week 12 assessment, a sensitivity analysis on a modified population will be performed. The modified full analysis set will include all patients who had a chance to complete the study before the termination date, i.e. who had been randomized at least 12 weeks before study termination date.

Similar considerations were made for the key-secondary endpoint.

Due to the considerably reduced number of patients who completed the study, only descriptive subgroup analyses will be provided. Moreover, the secondary endpoints will also be summarized descriptively only.

1 Introduction

This statistical analysis plan (SAP) describes all planned analyses for the Clinical Study Report (CSR) of study CEMA401A2202, a Phase 2, double-blind, placebo-controlled, randomized trial to determine the safety and efficacy of EMA401 in reducing 24-hour average pain intensity score in patients with painful diabetic neuropathy.

The content of this SAP is based on the final version of protocol CEMA401A2202 (release date 15-Sep-2017). All decisions regarding final analysis, as defined in the SAP document, have been made prior to database lock and unblinding of the study data.

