1.1 Study design

The study is interventional, randomized, parallel, placebo-controlled, double-blind treatment.

The study will consist of a Screening epoch (up to 4 weeks), a double-blind Treatment epoch (12 weeks), and a double-blind Treatment withdrawal epoch (1 week).

- Patients will be randomized in a 1:1 ratio to treatment with placebo or EMA401 100 mg b.i.d.

Overall approximately 400 patients will be enrolled in the study (i.e. approximately 200 patients will be enrolled in each treatment arm).

At Week 12 (Visit 199), all patients who completed the 12-week double-blind Treatment epoch will enter the 1-week double-blind Treatment withdrawal epoch. The IRT system will indicate the unique medication number for the package of study drug to be dispensed to the patient during the double-blind Treatment withdrawal epoch. This medication number will correspond to the blinded withdrawal regimen assigned at Baseline.

Randomization will be stratified by region (America, Europe and Australia) and use of concomitant pain medication for PDN (yes/no) in order to achieve balance of treatment allocation within the stratification factors.

[figure not shown]
Primary objective of this study is to compare the efficacy of EMA401 vs. placebo in 24-hour average pain intensity score at Week 12, using an 11 point Numeric Rating Scale (NRS) by testing the superiority of EMA401 100 mg b.i.d. vs. placebo.

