In the graphical testing procedure given in Figure 2-1, H1 and H2 denote the two null hypotheses of no treatment difference of EMA401 100 mg b.i.d. vs. placebo for the primary efficacy variable NRS and key secondary efficacy variable NPSI total score. The corresponding alternative hypotheses will be EMA401 100 mg b.i.d. is superior to placebo for the NRS and NPSI respectively. In the Figure 2-1 the number in the circle represents the proportion of alpha level to be assigned at the initial stage among the two null hypotheses. The direction and the number in the arrow represent the proportion of the alpha to be propagated to the next hypothesis. Initially, H1 will be tested at the full alpha level (1 sided) 0.025. If H1 is rejected then H2 will be tested also at the full alpha level (1 sided) 0.025.

To facilitate the interpretation of the estimated treatment difference a standardized effect size will be provided and will be calculated based on the results of the ANCOVA analysis.

The same ANCOVA model will be applied at the visits prior to Week 12. Multiplicity adjustment at visits prior to Week 12 will not be carried out.

Summary statistics for absolute values and change from baseline by treatment and visit will be provided for the original measurements (i.e. for the raw data prior to multiple imputation) of the primary efficacy variable. If a measurement is collected under the period of use of prohibited medications or the 7 days thereafter, it will be excluded from the summaries. ■

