2.5.4.2 Sensitivity analysis

A sensitivity analysis will be performed on the mFAS population using the same ANCOVA model as for the primary analysis.

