Since the NPSI has not been studied in the EMA401-003 study, to mitigate the risk of uncertainty on the value of treatment difference and standard deviation, the effect size (treatment difference/ standard deviation) of NPSI total score has been considered for the calculation of power. The power of the study was calculated for different effect sizes ranging in 0.1, 0.5 for NPSI total score corresponding to 100 mg.

Under the assumptions of a 0.8 point treatment difference between 100 mg b.i.d. and placebo, a standard deviation as 2.6 for the primary efficacy variable and an effect size of 0.4 for 100

[figure not shown]
mg b.i.d. for the key secondary variable, N=200 patients per treatment arm will provide approximately 85% power to show that 100 mg b.i.d. is statistically significant over placebo for the primary efficacy variable, using the testing procedure mentioned in Figure 2-1. The power of showing the statistical significance of 100 mg b.i.d. dose in terms of the key secondary variable will be 84% under the same scenario. If we assume the treatment difference of 0.7 for the NRS as observed in the 4-week PoC study and the effect size for NPSI as 0.35, then the power for the primary objective will be 77% and that for the key secondary objective will be 72%. If the treatment difference between 100 mg b.i.d. and placebo is 0.9 for the NRS, and effect size is 0.45 for 100 mg b.i.d. for the NPSI, the power increases to 94% for the primary objective. The corresponding power for the key secondary objective increases to 93%.

4 Change to protocol specified analyses

An additional population, the mFAS population, has been defined.

The following analyses were specified in the protocol but will not be performed due the early termination of study:

- first and third supplementary analysis to the primary analysis
- tipping point analysis
- supplementary responder analyses
- ANCOVA analyses for BPI-SF, worst NRS pain score, ISI, [REDACTED]
- proportional odds model for PGIC
- analyses regarding maintenance effect of EMA401 over placebo
- time to "sustained" pain reduction
- Apart from analyses of clinical abnormalities summaries of laboratory data, vital signs and ECG intervals have been removed
- Shift tables of laboratory data
- No safety figures will be presented
- Bazett correction for QTc

The following analyses have been added:

- sensitivity analyses on modified full analysis population
- analyses of TEAEs with onset before study termination date

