5.5.2 Secondary analysis

5.5.2.1 Logistic regression

The proportion of responders will be analyzed using a repeated measures logistic regression. The model is similar to the ANCOVA model:

Response = intercept + treatment + sex + age + PDNmed (yes/no) + baseline (mean pain intensity) + error.

The SAS procedure GENMOD will be used.

Odds ratios will be presented along with 95% confidence intervals and p-values for the treatment contrasts.

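### Does the SAP leave the EMA401–placebo difference without a confidence interval?

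*SAP*

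**What the plan says.** SAP 5.5.1.1 gives the ANCOVA for the primary analysis and for the other continuous variables. On output it says only: "The SAS procedure MIXED will be used for computing p-values and 95% confidence intervals for LS means." The contrast between arms is not mentioned there. The responder model in SAP 5.5.2.1 is worded more fully: "Odds ratios will be presented along with 95% confidence intervals and p-values for the treatment contrasts."

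For the NRS difference, SAP 2.5.2 sets a one-sided test at 0.025 and adds: "To facilitate the interpretation of the estimated treatment difference a standardized effect size will be provided." SAP 2.6.2 says that the NPSI treatment difference is estimated by the same method. Neither section names an interval for the difference, and neither does Protocol 9.4.2.

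Amendment 1 keeps the primary analysis and adds an analysis of the modified full analysis set (SAP 2.5.4.2): "A sensitivity analysis will be performed on the mFAS population using the same ANCOVA model as for the primary analysis." The preface to the amendment gives the purpose as "to get an idea about the effect that might be achieved if the trial had not been terminated". The programming detail sits outside the SAP (SAP 5.5): "SAS codes for all statistical methodology described in this section will be included as programming note in TFL Shells."

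On trial size, SAP 1.1 still reads "Overall approximately 400 patients will be enrolled in the study", and SAP 3 still reads "N=200 patients per treatment arm will provide approximately 85% power to show that 100 mg b.i.d. is statistically significant over placebo". The preface to Amendment 1 states that 137 of the 400 planned patients were randomised.

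**The concern.** The treatment difference is the primary result. In a trial stopped at about a third of its planned size, a reader needs its precision as much as its p-value. An LS mean belongs to one arm. Taken at face value, the ANCOVA section promises two arm intervals and no interval for the contrast, while a secondary responder analysis does get one. The mFAS analysis was added to give an idea of the effect, which makes the omission more noticeable.

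Arm intervals are a poor substitute. Each is narrower than the interval for the difference, and two arm intervals can overlap when the difference is significant. If only these were reported, a reader could misjudge both the precision and the result. Alongside this, the 400 and 200-per-arm text stands in an amended SAP with nothing to show that it is planning text.

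**Working it through.** **The planning figures.** Inputs from SAP 3: differences 0.7, 0.8 and 0.9; SD 2.6; 200 per arm; NPSI effect sizes 0.35, 0.40 and 0.45; correlation 0. One-sided alpha is 0.025 (SAP 2.5.2).

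- SE of the difference = 2.6 × √(2/200) = 0.26. Power = Φ(d/0.26 − 1.96).
- d = 0.7, 0.8, 0.9 give 76.8%, 86.8% and 93.3%. The SAP states 77%, 85% and 94%.
- Key secondary power is the primary power times the NPSI power (93.8%, 97.9%, 99.5%), that is 72.1%, 85.0% and 92.8%. The SAP states 72%, 84% and 93%.

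All agree to within two percentage points, so SAP 3 is a sound record of the design.

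**Interval widths at 137.** The arm split is not given, so 68 and 69 are assumed from the 1:1 allocation, with complete data, no covariate adjustment and t(135) = 1.978.

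| | SD 2.6 | SD 2.0 |
|---|---|---|
| SE of difference = SD × √(1/68 + 1/69) | 0.4443 | 0.3418 |
| Half-width, difference = 1.978 × SE | 0.88 | 0.68 |
| Half-widths, each arm = 1.978 × SD/√n | 0.624, 0.619 | 0.480, 0.476 |
| Arm intervals overlap up to (sum of the two) | 1.24 | 0.96 |

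The SD of 2.6 is the planning value. The SD of 2.0 is the value that SAP 3 reports from Study EMA401-003. The difference interval is about √2 = 1.41 times as wide as an arm interval, so the two are different quantities.

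Complete data is a favourable assumption, because the preface speaks of many discontinuations caused by the termination. If 60 to 120 patients carried effective Week 12 information (an assumed range), the half-width at SD 2.6 would be 1.96 × 2.6 × √(2/n), with n half that number: 1.32 down to 0.93.

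**Is the interval really missing from what the plan produces?** Three observations settle this.

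1. The phrase in SAP 5.5.1.1 governs p-values and intervals together. If it covered single-arm means only, the p-values would also be for single-arm means, each tested against zero. That is not H1 in SAP 2.5.2, which is no difference between EMA401 and placebo. The phrase has to reach the contrast for the p-value, and the same reading reaches it for the interval.
2. The analysis uses multiple imputation (SAP 2.5.2 and 5.5.1.2). A pooled test needs the pooled difference and its pooled standard error. The interval is the estimate plus or minus a t quantile times that standard error, with no further model to fit.
3. A reader holding the two LS means and the p-value can nearly rebuild the interval. With an observed difference of 0.9 at SD 2.6, t = 0.9/0.4443 = 2.026 and the half-width is 0.9 × 1.978/2.026 = 0.88, so the interval runs from 0.02 to 1.78. Combining the arm half-widths gives √(0.624² + 0.619²) = 0.88 here. In the real analysis that second route is approximate, because the LS means share covariates and jump-to-reference imputation uses placebo data for some EMA401 patients.

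A two-sided 95% interval matches the one-sided 0.025 test, so reporting it adds no second decision rule.

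**The case for a change.** The best case for a change is that a SAP should name its primary output before database lock. No sentence in either document names an interval for the ANCOVA difference. The SAP names one for the responder odds ratios, so its authors knew how to word it. The table shells are not among the documents, and a promise that they hold SAS code is not a promise of this output. Rebuilding the interval from a p-value works badly when the difference is near zero and the p-value is rounded.

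The textual part of this stands: the wording is incomplete. The step from there to a defect in the plan does not. The SAP commits to estimating the difference and testing it, and any standard output of the contrast from this fit carries its standard error and limits. Fuller wording in the responder section does not contradict shorter wording in the ANCOVA section. The argument from overlapping arm intervals fails because nothing in the SAP judges significance by overlap; SAP 2.5.2 fixes a test. Nor is the gap a product of the amendment: the listed changes include none to intervals, and Protocol 9.4.2 is silent on the same point.

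The reduced power at 137 patients is real. By the same normal formula, with 68.5 per arm and complete data, primary power over 0.7 to 0.9 is about 35% to 53% at SD 2.6 and 54% to 75% at SD 2.0. It has no bearing on whether an interval is named. It is also too favourable to write into SAP 3, given the discontinuations.

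**Conclusion.** No change is needed. SAP 5.5.1.1 leaves out a detail that the analyst will fill in the ordinary way: the LS-mean difference with its 95% interval, pooled over imputations, from the fit that gives the p-value. Following the plan as written still yields a valid one-sided 0.025 test and an estimated difference for NRS and for NPSI, so no result or conclusion would be wrong. The interval itself would be wide. At SD 2.6 it is about ±0.88 under complete data and an even split, which is comparable with the planned effects of 0.7 to 0.9, and it is wider if fewer patients contribute at Week 12. That width comes from stopping early and does not depend on the SAP's wording.

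The 400 and 200-per-arm text is a clerical matter. The Amendment 1 preface gives 137 of 400 planned, SAP 3 is a conditional statement of the design basis, and its figures reproduce. The conclusion assumes that the p-value refers to the contrast, as H1 requires. It does not depend on what the table shells contain.
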